Since curcumin has the ability to increase insulin sensitivity, improve β -pancreatic function and is considered a safe supplement by the FDA, it has been decided to include therapy based on oral consumption of curcumin in subjects with prediabetes who show resistance to insulin. This scheme will allow to attack metabolically the barriers previously presented, as well as overcome barriers due to the inability to adjust to lifestyle changes.

4. Hypothesis

Oral supplementation with curcumin will increase insulin sensitivity measured through homeostatic model HOMA-Beta and the Matsuda index.

5. Objectives

General: Determine the effects of oral supplementation with curcumin to improve insulin sensitivity through the homeostatic models HOMA β and Matsuda index.

Specifics

- a. Determine the effect curcumin supplementation on the levels of: glucose, insulin (pre- and post-prandial), glycosylated hemoglobin, blood pressure, insulin sensitivity, lipid level (e.g., cholesterol, triglycerides, high and low lipoproteins density) and anthropometric measures (weight, body mass index, waist-hip ratio).
- b. Determine the effect of oral curcumin supplementation on models of insulin resistance measured through HOMA-IR and insulinogenic index.
- c. Determine if the consumption of curcumin supplementation will decrease the levels of inflammation markers: PCR, IL1, IL-6, FNT α .
- d. Determine the safety of curcumin supplementation by measuring the existence of possible side effects.

Methodology

Type and design of the study

It is a randomized, double-blind, placebo-controlled clinical trial.

Population and sample size.

142 pre-diabetic patients will be included, with prior informed consent, according to the criteria of the ADA [6]. The subjects will be randomly assigned to the treatment group with curcumin (n = 71) or the placebo group (control group, n = 71) using a fixed randomization scheme with assignment based on random numbers generated by a computer.

The calculus of the sample was performed with the statistical program Gpower 3.1, which resulted in 71 individuals per group, to obtain a statistical power of 80% in difference of means between two independent samples with an effect size of 0.5 in a two-tailed test, contemplating a 10% of losses during the study period.

Criteria of inclusion, exclusion and elimination.

Inclusion Criteria

- Men and women with age between 18 and 60 years old.
- With prediabetes:
 - a) Fasting serum glucose: 100-125 mg/dL

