To achieve the goals of the study and the correct analysis of the data, the variables will be divided into two groups, with the primary ones being expected to be modified by the treatment in the first term, which will define the success or failure of the study. It is expected that the secondary variables may or may not be affected by the treatment. In addition, possible confounders that interfere with the response will be included in the analysis.

- *Primary variables:* post-prandial glucose (2 horas), HOMA-IR, HOMA-β, Matsuda index and insulinogenic.
- *Secondary Variables:* anthropometric measurements, serum lipids, each determination of blood chemistry.
- *Potential confounders:* age and gender.

To determine the statistical difference in the categorical variables between the group of curcumin and placebo, X² will be used. The continuous variables at the beginning and at the end between the two groups will be compared using t student test of independent samples and an analysis of covariance (ANCOVA), which will be adjusted by the initial values of the primary and secondary variables of interest. In addition, the percentage differences between the groups in the values of the primary variables will be analyzed, using values of adjusted covariates (including age, gender, BMI) such as 100 x (curcumin group-placebo group) / placebo group of each study variable.

Table 2. Activities to be carried out during the study period.

Activity	1 st Semester	2 nd Semester	3 rd Semester	Last bimester
Selection and recruitment of patients	→			
Intervention	→			
Anthropometric, clinical and biochemical determinations (markers of stress and inflammation)	→			
Opening of randomization keys			↓	→
Analysis and captured of results			→	
Results publication				→

Ethical and biosecurity aspects

During the development of the project, all determinations and processes will be carried out under the norms and statutes pre-established, dictated by the Ethics and Biosafety Committee of this Hospital. The potential risks of the intervention will be made known to the volunteers before the intervention, which include:

- a) From the sample taking. In each measurement period (initial, intermediate and final) blood sampling is required, which comprises approximately 60 ml, with the risks inherent to blood collection such as bruising and the elimination of contagion risk due to the use of disposable plastic material, new in each subject and in each shot.

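### The stated 80% power is for one t-test on an unnamed variable, but five primary variables decide success with no rule for combining them, so the 80% does not describe the declared criterion

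*Combined protocol and SAP*

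**What the plan says.** The Population and sample size section gives 71 participants per group, with 10% losses allowed for, to reach "a statistical power of 80% in difference of means between two independent samples with an effect size of 0.5" "in a two-tailed test". It names no outcome variable, time point or significance level, and gives no source for the effect size.

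The Statistical analysis section divides the variables into primary and secondary and describes "the primary ones being expected to be modified by the treatment in the first term, which will define the success or failure of the study". Five are listed as primary: 2-hour glucose, HOMA-IR, HOMA-β, the Matsuda index and the insulinogenic index. Groups are to be compared by an independent-samples t-test and by ANCOVA adjusted for initial values. The section does not say which of the two decides.

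Section 4 (Hypothesis) states that supplementation "will increase insulin sensitivity measured through homeostatic model HOMA-Beta and the Matsuda index", and the general objective in section 5 names the same two indices. No section states how many variables must be significant, in what order they are tested, or how the error rate is divided among them.

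**The concern.** A power figure belongs to a decision rule. This one was computed for a single comparison of two means, while the plan's stated basis for success is a set of five variables, or two if the hypothesis is taken as the criterion. The chance of meeting a multi-variable criterion can lie well below or well above the single-test figure, depending on the rule. Where it lies above, the type I error may no longer be the one used for sizing.

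Two things are at stake. A mixed result, such as Matsuda significant and HOMA-β not, has no pre-specified verdict. And a negative result could be read as coming from a trial with 80% power when the criterion actually applied had less.

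**Working it through.** **Inputs from the documents:** effect size 0.5, two-tailed, 80% power, 71 per group, 10% losses (Population and sample size); five primary variables (Statistical analysis); two indices (Hypothesis).

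**Assumptions, not in the documents:** alpha 0.05; a true effect of 0.5 SD on every variable; the same correlation ρ between every pair of test statistics; unadjusted t-tests.

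**Step 1: reproduce the plan's figure.** For a two-sample t-test with d = 0.5, two-sided alpha 0.05 and 80% power, the noncentral t distribution gives n = 63.8, so 64 per group. Allowing for losses, 64/0.9 = 71.1 and 64 × 1.1 = 70.4; either way about 71. Power at 64 per group is 80.1%. A one-sided test would need only 51 per group before losses, which does not fit. The 71 is therefore sound, and it is a single-test figure.

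**Step 2: set up the joint rules.** With n = 64 per group, each test statistic is approximately normal with mean 0.5 × √(64/2) = 2.83 and variance 1. The two-sided 0.05 threshold is 1.96, so single-test power is Φ(2.83 − 1.96) = 80.7% (80.1% with the exact t).

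- All k significant, ρ = 0: 0.807^k. This is 0.807² = 65% for two variables and 0.807⁵ = 34% for five.
- Any one of five significant when there is no effect, ρ = 0: familywise error 1 − 0.95⁵ = 22.6%.
- For ρ > 0, the same probabilities were integrated numerically over the equicorrelated normal distribution.

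**Step 3: results.**

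| Rule | ρ = 0 | ρ = 0.5 | ρ = 0.9 |
|---|---|---|---|
| HOMA-β and Matsuda both significant at 0.05 | 65% | 70% | 76% |
| All five significant at 0.05 | 34% | 53% | 70% |
| Any one of five at unadjusted 0.05: power | >99% | 98% | 90% |
| Any one of five at unadjusted 0.05: familywise error | 23% | 18% | 10% |
| At least one of five at Bonferroni 0.05/5 = 0.01 | 99% | 90% | 74% |

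Simulation with actual t-tests at 64 per group gave slightly lower values for the all-significant rules: 64% and 69% for two variables, and 33% and 51% for five, at ρ = 0 and 0.5.

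**Step 4: negative correlation for the pair.** By the formulas in the variable definitions, HOMA-β rises with fasting insulin and the Matsuda index falls. The two could therefore be negatively correlated in the hypothesised direction. At ρ = −0.3, −0.5 and −0.7 the both-significant power is 63%, 62% and 62%.

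**The case against.** The strongest reply is that the documents never say all variables must be significant. The analysis section says only that the primary variables define success, and the hypothesis can be read as naming two instruments rather than requiring a significant result on each. This stands. A reader might infer that the declared criterion has about 34-76% power and that the trial is underpowered. The documents do not support that: it presupposes an all-significant rule that is not written, and the range joins two different rules (five variables at correlation 0, two at 0.9).

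Nor is an uncorrected any-of-five rule the only one that keeps 80%. At least one of five at Bonferroni 0.01 controls the familywise error and still gives 99% at correlation 0, 90% at 0.5 and 84% at 0.7. It falls below 80% only at high correlations (79% at 0.8, 74% at 0.9).

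The planned ANCOVA also matters. Adjustment for a baseline correlated r with the outcome divides the mean of the test statistic by √(1 − r²). With r = 0.5, purely as an assumption, 2.83/0.866 = 3.27 and single-test power is Φ(3.27 − 1.96) = 90%; the pair then has 82-87% and all five 60-83% over correlations of 0 to 0.9. The documents give no baseline correlation and do not make ANCOVA the deciding analysis, so this gain is possible but cannot be credited.

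Finally, there is no arithmetic error in the 71 per group. None of these replies supplies the missing rule, and so none ties the 80% to the stated basis for success.

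**Conclusion.** The point holds as a mismatch between the power statement and the success criterion, not as a demonstrated power shortfall. The 80% is correct for one t-test at d = 0.5, an assumed two-sided alpha of 0.05 and 64 completers per group. It is not the power of a criterion resting on five variables, or on two, whose combination rule is unstated.

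The size of the gap depends on that rule. If all must succeed, power falls below 80% under the t-test assumptions: by about 4-15 points for the pair at correlations of 0 to 0.9 (80 − 76 to 80 − 65), and by about 10-46 points for all five (80 − 70 to 80 − 34). If any one of five suffices without adjustment, power exceeds the stated figure but the error rate is two to more than four times the assumed 5%. With Bonferroni, power may lie on either side of 80%.

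These are illustrations, not bounds. They rest on a common effect of 0.5, the assumed correlations and no baseline adjustment. The correction should be made because the plan as written leaves the choice among these rules open.

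**What to change.** In Population and sample size and in Statistical analysis, name the one variable, time point, test and alpha to which the 80% refers, for example the week-12 Matsuda index, baseline-adjusted, at two-sided alpha 0.05. State that this test alone decides success, and make the other four variables supportive. Word the hypothesis and general objective to match. The existing t-test calculation with 142 participants then supports the 80% at the design effect size, and any gain from baseline adjustment is extra.

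Otherwise keep 142 participants, state the all-or-any rule with its alpha allocation, and replace the unqualified 80% with the power of that rule, giving the correlation assumptions used.

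Either route is a change of wording, with no added participants or procedures. The cost is that four variables lose primary status, or that the stated power may be less favourable.

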 - b) Glycosylated hemoglobin (HbA1c): 5.7-6.4%
 - c) Post-prandial glucose: 140-199 mg/dL after an oral dose of 75 g of glucose.

Exclusion Criteria

- Subjects with any type of diabetes.
- Subjects with body mass index ≥ 35 kg/m²
- Pregnant Women.
- Volunteers who ingest drugs that alter blood glucose levels, antiplatelet agents, angiotensin-converting enzyme inhibitors, angiotensin II receptor antagonists, fibrates, statins.
- Subjects with serum creatinine > 2 mg/dL or in renal replacement therapy.
- Subjects that normally consume food supplements.
- subjects with acute infections or with chronic diseases (cancer, rheumatoid arthritis, etc.).

Elimination Criteria

- Patients that abandon treatment.
- Subjects that manifest any side effect (nauseas, diarrhea).
- Subjects that during the trial, show Diabetes mellitus diagnosis according to the ADA.

Definition of the variables to be evaluated and how to measure them

Nominals: Each variable is categorized and assigned a level (0 or 1) according to the information obtained in the questionnaires and the clinical results.

- Gender: Male (0) or Female (1)
- Treatment: placebo (0) or curcumin (1)
- Attachment to treatment: no (0), yes (1)
- Altered fasting glucose: no (0), yes (1)

Ordinals

- Body mass index. Is determined by measuring the weight (kg) and the size (m). It will be obtained dividing the weight by the squared size. It will consist of 5 levels: low weight (IMC <19), adequate weight (IMC: 19-24.9), overweight (IMC: 25-29.9), obese (IMC: 30-35), morbid obese (IMC >35).
- HbA1c. It will be determined in automatic equipment from a blood sample-EDTA in the central laboratory. Levels: low (<5.7), medium (5.8-6.4), high (>6.4).
- Fasting glucose and post-prandial glucose. It will be determined by evaluating the glucose tolerance curve after an oral dose of 75g of glucose. Every 30 min, for 2 hours, a peripheral blood sample will be obtained and the glucose concentration will be determined by automated equipment (Central Laboratory). The levels are the following:
Fasting Glucose (mg/dL): normal (<100), prediabetes (100-125), diabetes (>125).
Post-prandial Glucose (mg/dL) (2 horas): normal (<140), prediabetes (140-199), diabetes (>199).

Discontinue: Age, according to the given in the questionnaire.

Continues:

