- Anthropometric measurements: weight, height, waist circumference, hip circumference, waist-hip circumference ratio and body fat percentage. They will be measured using an electric bio impedance scale and a measuring tape.

- Clinical: It will be determined in the Central Laboratory by standard methods and/or automated equipment, and includes the following:
 - a) Systolic blood pressure and diastolic blood pressure.
 - b) Blood chemistry: insulin, triglycerides, cholesterol, HDL cholesterol, LDL cholesterol, uric acid, creatine, urea, BUN, alanine amino transferase, alkaline phosphatase, glutamyl transferase, lactic dehydrogenase, glycosylated hemoglobin, direct bilirubin, indirect bilirubin, total bilirubin.
 - c) Blood count
 - d) Inflammation markers: PCR, IL 1, IL6, TNF- α .
 - e) Glucose tolerance curve: Fasting serum glucose and at 30, 60, 90 y 120 min after the oral dose of glucose (75 gr).
 - f) Parameters of insulin resistance and sensitivity under the following formulas
 - g) HOMA-IR: $(\text{Insulin } \mu\text{U/ml})(\text{Glucose mg/dl})/405$.
 - h) Matsuda index: $10,000/\sqrt{[(\text{basal glucose})(\text{basal insulin})*(\text{glucose})(\text{insulin})]}$
 - i) Insulinogenic: $\Delta \text{ insulin}/\Delta \text{ glucose}$.
 - j) HOMA1-%B: $(20)(\text{FPI})/(\text{FPG} - 3.5)$

Procedure

Intervention

Participants who meet the inclusion requirements and wish to participate in the study will sign an informed consent. 142 individuals will be included, who will be randomized to receive curcumin (n=71) or placebo (n=71).

- All participants will receive the same diet and exercise indications for a period of three months after enrollment (before randomization).

- Regarding the diet, all patients who enter the research protocol will be assessed and supervised. The feeding plan will be prepared by a nutritionist, individually for each patient, based on the recommendations of the American Diabetes Association 2018, with the following: Carbohydrates 55%, proteins 20% and lipids 25%.

According to the needs of the patient, the quantity of kilocalories/day is calculated. For weight reduction 20 kcal/kg/day, weight maintenance 25 kcal/kg/day. Follow-up appointments will be made by nutrition: at the beginning, 4, 8 and 12 weeks after the start of the intervention.

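### Elimination after randomisation for stopping treatment, side effects or diabetes is undefined, and no rule keeps these participants in the week-12 comparison

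*Combined protocol and SAP*

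**What the plan says.** The Elimination Criteria list three events: "Patients that abandon treatment", "Subjects that manifest any side effect (nauseas, diarrhea") and "Subjects that during the trial, show Diabetes mellitus diagnosis according to the ADA". Nothing says whether elimination ends treatment, follow-up, inclusion in the analysis, or all three.

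Other sections that bear on the point:

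- **Statistical analysis.** Continuous variables are compared between arms at the start and at the end, by t-test and by ANCOVA adjusted for initial values. The primary variables are 2-hour glucose, HOMA-IR, HOMA-beta, the Matsuda index and the insulinogenic index. No analysis set, missing-data method or sensitivity analysis is given.
- **Definition of the variables.** The 2-hour glucose levels include "prediabetes (140-199), diabetes (>199") mg/dL. HbA1c has "Levels: low (<5.7), medium (5.8-6.4), high (>6.4"). Adherence is coded "Attachment to treatment: no (0), yes (1") but has no stated role in deciding who is analysed.
- **Table 1.** The glucose tolerance curve is taken at weeks 0 and 12 only. Biochemical measures are also taken at week 6, and the blood chemistry list includes HbA1c ("lactic dehydrogenase, glycosylated hemoglobin, direct bilirubin").
- **Population and sample size.** 71 per group, with 10% allowed for losses.
- **Objectives (Specifics, d) and Ethical and biosecurity aspects.** Side effects are an objective and are recorded on a sheet. Participants are told to stop treatment if a reaction occurs. Further follow-up is not mentioned.

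**The concern.** Randomisation makes the arms comparable at the start. Leaving people out because of something that happened afterwards, and that treatment may have influenced, undoes this. Neither the t-test nor ANCOVA on initial values restores it, because the selection acts on later events.

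The diabetes rule needs the most care because a primary variable can decide who is analysed. If curcumin lowers 2-hour glucose, more placebo than curcumin participants will exceed 199 mg/dL. Dropping them removes the evidence of benefit from the arm where it should show.

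The side-effect rule raises a separate problem. Safety is an objective, yet anyone with a side effect is eliminated and no safety set is defined. The 10% allowance for losses protects precision. It does not protect against selective removal.

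**Working it through.** **1. The plan's own figure.** A two-sample t-test with effect size 0.5, two-sided 5% (alpha is assumed; the plan does not state it) and 80% power needs 63.8, so 64 per arm. Then 64 × 1.1 = 70.4, rounded up to 71, and 64 / 0.9 = 71.1. The stated 71 reproduces. With nobody removed, power is 80% from 64 per arm and 84% from 71 per arm. The 71 figure applies if eliminations are the planned losses themselves; the 64 figure applies if they come on top.

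**2. Leaving out week-12 2-hour values above 199.** The documents give no mean or SD, so these are assumptions: normal values, placebo mean 130 to 150 mg/dL, SD 25 to 30, true benefit 0.5 SD. The cut is 199.5, for values reported in whole mg/dL.

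For an arm with mean m and SD s, let a = (199.5 − m)/s and λ = φ(a)/Φ(a). The mean of those kept is m − sλ, and the share removed is 1 − Φ(a). The proportional shrinkage of the difference is (λ placebo − λ curcumin)/0.5.

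| | Mean 130, SD 25 | Mean 150, SD 30 |
|---|---|---|
| a, placebo / curcumin | 2.78 / 3.28 | 1.65 / 2.15 |
| λ, placebo / curcumin | 0.0084 / 0.0018 | 0.1076 / 0.0402 |
| Removed, placebo / curcumin | 0.3% / 0.05% | 5.0% / 1.6% |
| True difference (mg/dL) | 12.5 | 15.0 |
| Difference among those kept (mg/dL) | 12.3 | 13.0 |
| Shrinkage | 1.3% | 13.5% |
| Power from 64 per arm | 79.6% | 73.0% |
| Power from 71 per arm | 83.6% | 77.4% |

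Power uses the noncentral t with the reduced variances and the expected numbers kept.

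For ANCOVA with an assumed baseline correlation of 0.5, simulation gives shrinkage of about 1 to 10% over the same two cases. Power falls by at most 4 to 5 percentage points, from about 90% (64 per arm) or 92 to 93% (71 per arm).

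**3. Where in that range.** Under Intervention, all participants receive diet and exercise indications for three months before randomisation. Any benefit from that lowers the week-12 mean and points to the lower end. In the other direction, inclusion criterion c) is "Post-prandial glucose: 140-199 mg/dL after an oral dose of 75 g of glucose", but the plan does not say whether every participant must meet it.

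**4. The other four primary indices.** Take an index with within-arm correlation r with 2-hour glucose. The mean of those kept moves by −rλ in SD units. At mean 150, SD 30, λ differs between arms by 0.1076 − 0.0402 = 0.0674. For an index that treatment lowers by 0.5 SD:

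- r = +0.3 to +0.7: the difference shrinks by 0.0674r/0.5, which is 4 to 9%.
- r = −0.3 to −0.7: the difference grows by 4 to 9%.

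The documents give the sign of neither the correlation nor the treatment effect in a form that settles this. HOMA-beta shows the difficulty. The plan's formulas make HOMA-IR and HOMA-beta both proportional to fasting insulin, so a fall in insulin lowers both, whereas the Hypothesis uses HOMA-beta as a measure of improved sensitivity.

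**5. Side effects.** The Background cites a study with side effects in under 1% of its sample. Suppose 1% of the curcumin arm is removed, those removed are 0.3 to 0.5 SD worse than the rest, and there is no true effect. The bias is 0.01 × 0.3 to 0.01 × 0.5, or 0.003 to 0.005 SD, and the false-positive rate is 5.0%.

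**The case against.** The strongest reply is that the plan never says eliminated participants leave the analysis. The Ethical section treats the same reactions as a reason to stop capsules, so elimination might be only a stopping rule. A *no* code for adherence would also be of little use if everyone who abandoned treatment were removed. This stands as far as it goes: a completers-only analysis is an inference, not a stated plan. But someone who has already abandoned treatment cannot then be eliminated from treatment, so the word must mean more than stopping capsules. No section supplies the opposite rule either.

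Second, the plan does not say that one final value above 199 mg/dL is an ADA diagnosis. Its glucose levels categorise a variable; the elimination rule refers to a diagnosis. That also stands. The calculation in step 2 shows what follows if such values are dropped, not what will happen. If only diagnoses before week 12 count, the visible route is HbA1c at week 6, and those participants could have no post-baseline curve at all.

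Third, a reader might infer a large loss of power, a uniform dilution across all five primary variables, or a materially inflated false-positive rate. The documents support none of these. Large shrinkage would need week-12 placebo means well above 150 mg/dL, for which there is no basis. Uniform dilution fails on the signs in step 4. A raised false-positive rate would need removal from one arm far above the cited rate, and capsules are blinded and colour-matched.

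**Conclusion.** The concern holds as a gap that should be fixed, not as a demonstrated analysis error. Three post-randomisation events eliminate participants, elimination is undefined, and nothing keeps those participants in follow-up or in the comparison. As naturally read, the week-12 comparison is not between the randomised groups.

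If week-12 values in the diabetes range are left out, a true benefit on 2-hour glucose is diluted by about 1 to 14%. Power of the t-test then falls from 80% to 73 to 80%, or from 84% to 77 to 84%, and the pre-randomisation diet and exercise period favours the milder end. For HOMA-IR, HOMA-beta, Matsuda and the insulinogenic index the direction is unknown. Removal for side effects at the cited rate has a negligible effect. Unequal abandonment could bias in either direction, and the documents give no rate for it. The net direction over all three rules is therefore unknown.

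All means, SDs, correlations and the 5% level are assumptions. Confidence is medium because the main uncertainty is what the sponsor meant by elimination.

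**What to change.** Add to the protocol and to its Statistical analysis section: *Meeting an elimination criterion after randomisation does not remove a participant from the analysis. All randomised participants are analysed in their assigned arm, and every observed week-12 value is included, including values in the diabetes range.*

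Then:

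- Seek the scheduled week-12 measurements from participants who stop capsules, where they agree and clinical care allows. No rule on stopping or care changes. If the curve is not taken, treat its values as missing.
- Name one method for missing week-12 values, such as multiple imputation from baseline and available week-6 data, with one sensitivity analysis for data not missing at random.
- Report side effects and diabetes diagnoses by arm among all who took at least one capsule.
- Keep the completer or adherent subset as a sensitivity analysis.

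The cost is a few sentences, a few more week-12 visits (some participants will decline) and some analysis work. The effect estimate may be smaller because non-adherent participants are included.

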The therapeutic strategies for prediabetes to this day are based on the change of habits, mainly food and exercise plans. It has been advice, in specific circumstances, to grant a pharmacological regimen. Studies sustain that the execution of a restrictive plan of exercise and food quality reduces the risk of DM2 between 40 al 70%, regardless of age, sex and racial condition (6). Pharmacotherapy (metformin and pioglitazone, mainly) is reserved for the treatment of patients with prediabetes who meet the following conditions: Body mass index > 35 kg/m², Women with previous gestational diabetes and patients under 60 years of age that meet any of the previous criteria (7). Pharmacotherapy represent a higher cost for the health sector, patients usually leave treatment due to secondary reactions and poor clinical management of doses (8, 9). The approach now is to identify new effective

therapeutic agents, with a relatively low cost and toxicity, that can be used regularly to control DM2 progression in the pre-diabetic population.

Sensitivity and insulin resistance.

Insulin resistance is the initial characteristic of metabolic alterations, that lead to the development of prediabetes and type 2 diabetes mellitus.

The hyperinsulinemic euglycemic clamp technique (clamp) is the gold standard for measuring insulin resistance. However, it is only used in the field of scientific research due to its complexity, probable adverse effects and economic cost.

Among the indirect methods, most commonly used to measure insulin resistance, is the homeostatic model assessment of insulin resistance (HOMA-IR), which is derived from a mathematical evaluation, and is used to generate an estimate of insulin sensitivity through the measurement of fasting plasma glucose and insulin levels. (10). The correlation between the estimates of IR derived from HOMA and the euglycemic impingement is described in different studies (Rs 0,88, P <0,0001(10); Rs 0,85, P < 0,0001(11)).

The equation is simplified to:

$$\text{HOMA-IR: } (\text{FPI})(\text{FPG}) / 405$$

Where FPI is the fasting plasma insulin concentration (mU/l) and FPG is the fasting plasma glucose concentration (mmol / l)(10).

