Other indirect methods for measuring insulin resistance use data derived from the oral glucose tolerance curve, which is a simple, non-invasive, physiological and inexpensive test, widely used in clinical practice to diagnose intolerance and diabetes mellitus type 2, as well as in the determination of insulin sensitivity in epidemiological, population and large-scale intervention studies. After a night of fasting, a 75g load of oral glucose is administered and the basal glucose and insulin concentrations are determined at 30, 60 and 120 minutes after the dose is applied. Derived from this information, various indices have been developed, among them the Matsuda index (12). Insulin sensitivity derived from these formulas correlates well with hyperinsulinemic euglycemic clamping.

Oral supplementation with Curcumin.

Curcumin or Curcuma Longa ((1E,6E)21,7-bis(4-hydroxy-3-methoxyphenyl)-1,6-heptadiene-3,5-dione), is the main ingredient of the Hindu condiment, Turmeric, which is obtained from the Rhizome plant. In new studies, it has been documented that the oral consumption of curcumin (Curcuma longa) in pre-diabetic and diabetic patients has a positive effect as an antidiabetic agent thanks to its anti-inflammatory, antioxidant, antithrombotic, cardio and neuroprotective effects (13-15). In animal models, it has been shown that oral curcumin consumption is capable of increasing insulin sensitivity in liver, muscle and adipose tissue (16-18), increases glucose uptake in muscle (17) and insulin secretion (19,20), which is reflected in the reduction of hyperglycemia, glycosylated hemoglobin, decrease of the homeostatic model assessment of insulin resistance (HOMA-IR) and decrease of serum lipids (21). Many of these actions are performed by turning on the endogenous antioxidant battery and decreasing the pro-inflammatory proteins, thanks to its ability to modulate protein homeostasis.

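### Do the mixed glucose units in the HOMA formulas put the primary HOMA-beta analysis at risk?

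*Combined protocol and SAP*

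**What the plan says.** The section of the Background on insulin sensitivity and resistance prints HOMA-IR as FPI times FPG over 405 and then defines the symbols: "Where FPI is the fasting plasma insulin concentration (mU/l) and FPG is the fasting plasma glucose concentration (mmol / l". This is the only place where FPI and FPG are defined.

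The section that defines the variables (Clinical) lists the formulas to be used. Item g is HOMA-IR with its own labels and units: insulin in µU/mL, and for glucose "Glucose mg/dl})/405". Item j returns to the symbols FPI and FPG: "HOMA1-%B: $(20)(\text{FPI})/(\text{FPG} - 3.5". It prints no unit and no conversion. The same section classifies fasting glucose in mg/dL: "Fasting Glucose (mg/dL): normal (<100), prediabetes (100-125), diabetes (>125".

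The Statistical analysis section names the primary variables: "post-prandial glucose (2 horas), HOMA-IR, HOMA-β, Matsuda index and insulinogenic". HOMA-beta also appears in the hypothesis and the general objective.

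On the glucose curve, the Background speaks of samples at 30, 60 and 120 minutes. Item e of the Methods has "Fasting serum glucose and at 30, 60, 90 y 120 min after the oral dose of glucose (75 gr".

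**The concern.** The divisor 405 cannot be right for both mmol/L and mg/dL, so the Background and item g contradict each other. The symbol FPG then reappears in a primary variable without a unit. Its only definition stands beside an equation in which that unit is wrong, and the glucose limits and the HOMA-IR formula three items earlier use mg/dL. An analyst could plausibly put mg/dL values straight into item j.

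The stakes would be more than cosmetic. The offset of 3.5 mmol/L corresponds to 63 mg/dL. Subtracting only 3.5 from a value in mg/dL nearly removes the offset, and the index becomes almost proportional to FPI/FPG. Because that distortion varies with glucose, it would carry into the t-test, the ANCOVA and the percentage difference for a variable on which the trial is to be judged.

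**Working it through.** **Inputs.** From the documents: the three formulas above and the fasting criterion of 100–125 mg/dL. Assumed: 1 mmol/L of glucose = 18 mg/dL (18.016 is also tried), and illustrative insulin levels of 10 and 15 µU/mL. Insulin in mU/L and in µU/mL is numerically the same. The plan prints no computed HOMA value, so there is no figure of its own to reproduce.

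**Constants.** 405/18 = 22.5, 3.5 × 18 = 63 and 20 × 18 = 360. Item j in mmol/L therefore equals 360 × FPI/(FPG − 63) with FPG in mg/dL.

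**Values at FPI = 10.**

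| FPG, mg/dL | 100 | 110 | 125 |
|---|---|---|---|
| FPG, mmol/L | 5.56 | 6.11 | 6.94 |
| HOMA-IR, item g (mg/dL, 405) | 2.47 | 2.72 | 3.09 |
| HOMA-IR, Background read literally (mmol/L, 405) | 0.137 | 0.151 | 0.171 |
| HOMA-beta, item j in mmol/L | 97.3 | 76.6 | 58.1 |
| HOMA-beta, item j with mg/dL entered | 2.07 | 1.88 | 1.65 |
| HOMA-beta ratio, correct to mis-entered | 46.9 | 40.8 | 35.3 |

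**HOMA-IR.** The two versions differ by exactly 18 at every glucose level. Multiplying every value, baseline included, by one constant changes neither the t statistic nor the ANCOVA test of treatment. It also leaves 100 × (curcumin − placebo)/placebo unchanged. Item g needs no correction.

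**HOMA-beta.** The ratio is 18 × (FPG − 3.5)/(FPG − 63), in which insulin cancels. For example, at 100 mg/dL it is 18 × 96.5/37 = 46.9. With 18.016 the three ratios are 47.1, 40.9 and 35.3. Since the ratio is not constant, a mis-entry would not cancel:

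- Insulin unchanged, FPG from 110 to 100: 47/37 − 1 = +27.0% in correct units, against 106.5/96.5 − 1 = +10.4%.
- Over the same fall in FPG, the two versions move in opposite directions if insulin falls by more than 1 − 96.5/106.5 = 9.4% and less than 1 − 37/47 = 21.3%.

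**Which unit item j requires.** Two independent clues agree. The only definition of FPG is mmol/L. The constant points the same way: at 110 mg/dL, an offset of 3.5 mg/dL is 3.5/110 = 3.2% of the value and would do almost nothing, whereas 63/110 = 57.3% is a working offset. The label as a percentage also fits results of 58 to 97 and not results of about 2.

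**Would a mis-entry be seen?** At FPI = 15 and FPG = 110, the correct value is 300/(6.111 − 3.5) = 114.9 and the mis-entered value is 300/106.5 = 2.8. Every participant would be low by a factor of roughly 35 to 47 over the fasting range. Glucose and insulin are both measured variables in their own right, so the index can be recomputed without loss of data.

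**Sampling times.** The Background sentence with 30, 60 and 120 minutes describes the test in general. In the Methods, the description of fasting and post-prandial glucose under Ordinals has half-hourly samples over two hours, which agrees with item e.

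**The case for a change.** The strongest case for acting is that a primary formula should not need inference. The Background unit is wrong where it stands, so a reader may distrust it. An editor who corrected it to mg/dL to match item g, and stopped there, would remove the only support for reading item j in mmol/L. The resulting error would depend on glucose and could reverse the direction of the effect when glucose and insulin fall together, a plausible pattern for an agent expected to raise insulin sensitivity. A unit label costs nothing.

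The facts in this stand: the Background slip is real, item j lacks a printed unit, and a mis-entry would not cancel. What does not stand is that the plan leads the analyst there. Item g carries its own labels and units, whereas item j uses symbols defined as mmol/L, and 3.5 confirms that reading even if the definition is doubted. The half-finished edit is a hypothetical future mistake, not a fault in the present text.

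Two further gaps can be raised. The second glucose and insulin pair in the Matsuda formula (item h) is not defined as printed, but a bar for the mean may have been lost when the PDF was read, so this cannot be held against the plan. The insulin sampling times and the interval for the deltas in the insulinogenic index (item i) are not spelled out. The objectives do call for insulin before and after the load, and the resources section lists the insulin assay among the materials for the glucose curve. What is missing there is detail, and it is separate from the unit question.

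**Conclusion.** No change to the plan follows. Followed as written, items g and j give sound HOMA-IR and HOMA-beta values. The contradiction is confined to a Background equation that no analysis uses, and its 18-fold factor would cancel in the planned comparisons even if that version were applied throughout. Item j lacks a unit that its constant and the only definition of FPG both supply, and an analyst who knows the index fills that gap correctly.

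The possible error is large in level (46.9 to 35.3 times over 100–125 mg/dL) and not constant, but it needs a step the plan does not direct and would show at once in the results. The conclusion rests on the conversion of 18 mg/dL per mmol/L, on the illustrative insulin levels for the absolute values only, and on the analyst noticing HOMA-beta values near 2 for an index expressed as a percentage. Printing the unit beside item j would be good housekeeping but would alter no planned result.
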